10.1. Initial Submission

The sponsor-investigator and/or study team members (as applicable) prepare and submit the initial application to the FDA, and maintain copies of all communications and correspondence between the FDA and sponsor-investigator. The FDA acknowledgment letter lists the assigned IND number and a statement that the IND will become active if the sponsor-investigator does not hear back from the FDA within 30 days of the date of receipt.

- The date of the acknowledgement letter is used as the IND activation date if further correspondence from the FDA is not received.
- If further communication is required, and all issues have been resolved, the FDA will send a letter stating that the clinical investigation may begin, including the IND activation date.

The sponsor-investigator maintains all FDA documentation, specifically the IND activation date, in the regulatory files.

10.2. Amendments

When necessary, the sponsor-investigator and/or study team members (as applicable) prepare and submit protocol amendments. Once submitted to the FDA, the FDA will not respond unless requested.

10.3. Safety Reports

The sponsor-investigator and/or study team members (as applicable) prepare and submit any serious, unexpected and related adverse events to the FDA, and all participating investigators, in an IND safety report.

Adverse Events that are:	Notify:

 • Serious • Suspected/Related • Unexpected 	FDA and all participating institutions as soon as possible, but no later than 15 calendar days after learning of the event

 • Serious 
 ◦ Life-threatening or Fatal • Suspected/Related • Unexpected 	FDA and all participating institutions within 7 calendar days after learning of the event

10.4. Annual Reports

Within 60 days of the anniversary date that the IND application went into effect, the sponsor-investigator and/or study team members (as applicable) prepare and submit the annual report. Once submitted to the FDA, the FDA will not respond unless requested.

11. STATISTICAL CONSIDERATIONS

11.1. Study Hypotheses

We hypothesize that the combination of radiation, NKTR-214, and anti-PD-1 checkpoint blockade will improve efficacy compared to the pembrolizumab arm of Keynote 048. Given the non-redundant immune modulatory roles of radiation, NKTR-214, and anti-PD-1 checkpoint blockade, our secondary hypotheses are that this combination will be effective in generating an anti-tumor immune response against recurrent/metastatic head and neck squamous cell carcinoma resulting in an ORR $\geq 44\%$ with good patient reported quality of life and with correlative evidence demonstrating a more diversified and activated adaptive anti-tumor immune response.

11.2. Sample Size Considerations

This study will enroll 24 participants to test the hypothesis that the combination of NKTR-214 with palliative radiation and anti-PD-1 therapy results in an ORR $\geq 44\%$. Under the null hypothesis for ORR ≤ 0.22 , based on one-sided one sample proportion test with type I error of 0.1, the expected power levels to detect alternative ORRs of 0.35, 0.4, and 0.45 are 55 %, 74 %, 87 % respectively. The null hypothesis will be rejected and superiority concluded if 8 or more responses are observed in 24 participants. This design yields a type I error rate of .04 and power of .8 when the true response rate is 44 %.

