1.2. Rationale

Based on the available clinical data and preclinical data, we hypothesize that the combination of palliative radiation, NKTR-214, and anti-PD-1 checkpoint blockade will improve the ORR compared to a 22 % estimated ORR (based on historical data outlined above) for pembrolizumab alone or pembrolizumab plus palliative radiotherapy in patients with metastatic or recurrent HNSCC. Given the non-redundant and potentially synergistic immunologic effects of radiation, NKTR-214, and anti-PD-1 checkpoint blockade, our primary hypothesis is that this combination will be effective in generating an anti-tumor immune response against recurrent/metastatic HNSCC resulting in ≥ 44 % ORR. We further anticipate a rate of ≤ 25 % unexpected grade 3 toxicity with good patient-reported HRQoL and with correlative evidence demonstrating a more diversified and activated adaptive anti-tumor immune response. Because many side effects related to IL2 based therapies are predictable, transient, and manageable, they should not limit the evaluation of overall safety or therapeutic efficacy.

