11.3.1. Analysis Plans for Primary Objective

ORR will include confirmed complete response (CR) + confirmed partial response (PR) and will be assessed based on RECIST 1.1 criteria. ORR will be reported with the 95 % confidence interval (CI). Progression of any radiated tumors will be considered in this evaluation but response of radiated tumor(s) will not be considered as evidence of response for the purpose of this study unless all tumor sites are radiated.

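### Section 11.2 says the trial tests ORR ≥ 44%, but its null and decision rule test only ORR > 22%, and Sections 1.2 and 11.1 disagree on the primary hypothesis and its benchmark

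*Combined protocol and SAP*

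**What the plan says.** - **Section 11.2** says the trial will "test the hypothesis that the combination of NKTR-214 with palliative radiation and anti-PD-1 therapy results in an ORR" of at least 44%. It then sets the null at ORR ≤ 0.22, to be tested one-sided with a one-sample proportion test at 0.1. The rule is: "The null hypothesis will be rejected and superiority concluded if 8 or more responses are observed in 24 participants". The figure of 44% returns only as the true rate at which a power of 0.8 is claimed.
- **Section 3** repeats the 22% null, the 8-of-24 rule and the 44% power figure, without saying that 44% is the hypothesis under test.
- **Section 1.2** contains two hypotheses. The first is an improvement on an estimated 22% for pembrolizumab with or without palliative radiotherapy. The second reads "our primary hypothesis is that this combination will be effective in generating an anti-tumor immune response" and, later in the same sentence, "recurrent/metastatic HNSCC resulting in ≥ 44 % ORR".
- **Section 11.1** leads with the hypothesis that the combination "will improve efficacy compared to the pembrolizumab arm of Keynote 048". Section 1.1.2 gives 17% for pembrolizumab alone in that study. Section 11.1 then says "our secondary hypotheses are that this combination will be effective in generating an anti-tumor immune response", and the ≥ 44% target sits in that sentence.
- **Section 11.3.1** asks for the ORR with a 95% confidence interval. It names no method and does not link the interval to the decision.

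**The concern.** A design alternative is not a tested hypothesis. Rejecting ORR ≤ 22% supports ORR > 22% and nothing higher. Powering at 44% against a 22% null is ordinary single-arm practice; the fault is the sentence in Section 11.2 that presents the planning rate as the thing being tested. No section gives a criterion for concluding that the ORR is at least 44%.

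The sections also disagree on which hypothesis is primary and what the comparator is. A reader of the final report could take success to mean above 17%, above 22%, or at least 44%. These are different claims, and the minimum successful result supports them to very different degrees. This is the primary endpoint of an uncontrolled trial judged against history, so the benchmark defines what a positive result means.

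**Working it through.** **Inputs.** n = 24, null 0.22, one-sided 0.10, cut-off 8 and planning rate 0.44 (Section 11.2); 17% for pembrolizumab alone (Section 1.1.2); 95% CI (Section 11.3.1). The interval method is not named, so I use Clopper-Pearson and note the others.

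**Formulas.** With X ~ Binomial(24, p):
- P(X ≥ r | p) = Σ from k = r to 24 of C(24, k) p^k (1 − p)^(24 − k).
- The exact 95% limits for x responses solve P(X ≥ x | lower) = 0.025 and P(X ≤ x | upper) = 0.025.
- The exact one-sided 90% lower bound solves P(X ≥ x | bound) = 0.10. It equals the lower limit of the two-sided 80% interval.

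**1. The plan's own figures.** The quoted powers of 55%, 74% and 87% at 0.35, 0.40 and 0.45 reproduce with the arcsine approximation against a null of 0.22 at one-sided 0.10: Φ(2√24[arcsin√p − arcsin√0.22] − 1.2816) gives 55.5%, 74.0% and 87.3%. They are therefore powers of a test against 22%. The figures attached to the 8-of-24 rule do not reproduce:

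| Quantity for ≥ 8 of 24 | Stated | Exact |
|---|---|---|
| Type I error at 22% | 0.04 | 0.138 |
| Power at 44% | 0.80 | 0.897 |

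**2. What the minimum success shows.** 8/24 = 33.3%, which is 44 − 33.3 = 10.7 points below 44%. The 95% interval is 15.6–55.3% (exact), 18.0–53.3% (Wilson) or 14.5–52.2% (Wald). Each contains 17%, 22% and 44%. The result is compatible with 44% but does not establish it.

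**3. The benchmark matters.** The exact one-sided p for 8/24 is P(X ≥ 8 | p):
- against 17%: 0.039;
- against 22%: 0.138.

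The same result is below 0.10 against the comparator named in Section 11.1 and above 0.10 against the null in Section 11.2.

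**4. Success when the ORR is below 44%.** P(X ≥ 8) is 56% at a true ORR of 0.33, 64% at 0.35 and 81% at 0.40. These rates all exceed 22%, so frequent rejection is expected. They show only that rejection does not separate 44% from lower rates.

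**5. What a test of 44% would need.** For a null of ORR ≤ 44% at one-sided 0.10, P(X ≥ 14 | 0.44) = 0.114 and P(X ≥ 15 | 0.44) = 0.053. The cut-off would be 15 of 24 (62.5%), against the written 8.

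**6. The bound that matches the 0.10 test.** Nine responses are shown for comparison only; the plan does not state that cut-off.

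| Responses | ORR | P(X ≥ x given 22%) | One-sided 90% lower bound |
|---|---|---|---|
| 8 | 33.3% | 0.138 | 20.5% |
| 9 | 37.5% | 0.062 | 24.1% |

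The bound excludes 22% exactly when the p-value against 22% is below 0.10, which happens from 9 responses upward.

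**The case against.** The strongest reply is that the operative design is explicit. Sections 3 and 11.2 give the null, direction, alpha and rule, and define success as rejecting ORR ≤ 22%. The protocol summary describes ORR as compared with historical control data, and Section 1.2 also hypothesises improvement over 22%, which matches the null. On this view one sentence is loose and no analysis changes. It is right that the tested null is stated, and that a cut-off below the planning rate, with a wide interval around it, is normal at n = 24.

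Three stronger readings are tempting, and the documents do not support them:

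- A reader might infer that the trial would announce its ≥ 44% hypothesis as met after 8 responses. No section says so; the stated conclusion is superiority over the 22% null.
- A reader might infer that the 95% CI will include 22% whatever cut-off is used. It does not: at 10/24 the exact interval is 22.1–63.4%.
- A reader might blame the overlap with 22% at 8/24 on setting a 95% interval beside a one-sided 0.10 test. That pairing is common practice, and at 8/24 the matching bound (20.5%) is also below 22%. The overlap there comes from the rule.

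What the reply does not remove is that Section 11.2 names a tested hypothesis which its design does not test, and that Sections 1.2 and 11.1 conflict on rank and comparator.

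**Conclusion.** The point stands as a fault in the stated hypothesis and benchmark. The design tests ORR > 22%; the text of Section 11.2 says it tests ORR ≥ 44%; Section 1.2 calls ≥ 44% primary, and Section 11.1 calls it secondary while pointing to a comparator reported at 17%. The minimum success would not by itself establish 44%, and whether it is significant at 0.10 depends on which benchmark is meant.

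This rests on exact binomial calculation with all 24 participants in the denominator, and on the written cut-off of 8. The conclusion about the hypotheses does not depend on the interval method. The type I error of 0.138, against a stated 0.04 and a nominal 0.10, is a separate error. Correcting the cut-off would not reconcile the hypotheses, and reconciling the hypotheses would not correct the cut-off.

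**What to change.** 1. In Sections 1.2, 11.1 and 11.2, state one primary hypothesis: null ORR ≤ 22% against ORR > 22%. Describe 44% as the planning alternative only. In Section 11.1, replace the Keynote-048 arm as benchmark with the 22% rate, or explain how the two relate.
2. Say that success means the ORR exceeds 22%, and that it is not in itself evidence of an ORR of 44% or more.
3. In Section 11.3.1, keep the 95% CI, name its method, and add the exact one-sided 90% lower bound that matches the 0.10 test.
4. Correct the decision rule and its stated error rates in Sections 3 and 11.2 as a separate change. Without it, the added bound would contradict a declared success at exactly 8 responses.

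Items 1 to 3 cost some wording and one extra figure in the results table, with no added participants, visits or data. The downside is a more modest claim on success.

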11.3. Final Analysis Plan

Any subject who receives at least one dose of NKTR-214 on this protocol will be evaluable for ORR. All subjects with measurable disease who have received at least one cycle of treatment and have their disease re-evaluated will be evaluable for assessment of objective response.

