Anti-PD1	Anti-program death one
PEG	Polyethylene glycol
PFS	Progression-free Survival
PHI	Protected Health Information
PI	Principal Investigator
PR	Partial Response
PRC	Pharmaceutical Research Center
PSR	Protocol Summary Reports
PTV	Planning Target Volume
RECIST	Response Evaluation Criteria in Solid Tumors
RT	Radiation Therapy
SAE	Serious Adverse Event/Serious Adverse Experience
SD	Stable Disease

SOC	Standard of Care
SOP	Standard Operating Procedure
ULN	Upper Limit of Normal
UP	Unanticipated Problem
UW	University of Wisconsin
UWCCC	University of Wisconsin Carbone Cancer Center
WBC	White Blood Cell
WOCBP	Women of Childbearing Potential

PROTOCOL SUMMARY

Title: *Phase II Study of Bempegaldesleukin (NKTR-214) Together with Palliative Radiation and anti-PD-1 Checkpoint Blockade in Patients with Recurrent or Metastatic Head and Neck Squamous Cell Carcinoma*

Précis: This is a Phase II study of NKTR-214 in combination with palliative radiation and anti-PD-1 checkpoint blockade in patients with recurrent or metastatic head and neck cancer. For all enrolled participants, cycle 1 consists of anti-PD-1 therapy and NKTR-214, followed by palliative radiation combined with anti-PD-1 therapy and NKTR-214 in cycle 2. In subsequent cycles participants will receive NKTR-214 and anti-PD-1. Participants who have one or more sites in need of palliative radiation therapy who have not received previous PD-1 directed therapy are eligible. The phase II study will enroll 24 subjects with a primary endpoint of overall response rate.

Objectives:

Primary Objective:

- Evaluate the objective response rate (ORR) to NKTR-214 in combination with anti-PD-1 therapy and palliative radiation in the efficacy-evaluable population.
 - *Outcome measure:* ORR will include confirmed complete response (CR) + confirmed partial response (PR) and will be determined as per RECIST1.1, by investigator assessment.

Secondary Objectives:

- Determine the safety, as well as, the progression free survival (PFS), overall survival (OS), clinical benefit (CB, defined as CR + PR + stable disease at \geq 6 months (SD)), and duration of response with NKTR-214, anti-PD-1, and palliative radiation in the efficacy-evaluable population
- *Outcome measures:*
 - Toxicities \geq Grade 3 is defined by the NCI Common Terminology Criteria for Adverse Events (CTCAE) version 5.0. Toxicities not "unrelated" to treatment, will be considered treatment-related.

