6.8. Final Study Visit or Withdrawal Visit

If the participant decides they no longer wish to participate in study follow-up, that visit will constitute the final study visit. Otherwise, the final study visit will occur at the completion of long-term follow-up, as noted above.

- Record AEs as reported by participant or observed by investigator (RR for NKTR-214, SOC for anti-PD-1 and RT)
- Collect HRQoL questionnaire (RR)
- Perform physical examination (SOC)

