12.8. Definitions for Response Evaluation – RECIST 1.1

12.8.1. Objective Response Rate

The objective response rate is the proportion of all subjects with confirmed PR or CR according to RECIST 1.1, from the start of treatment until disease progression/recurrence (taking as reference for progressive disease the smallest measurements recorded since the start of treatment).

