⁵Subjects without documented disease progression will be followed for disease progression every 4 months \pm 30 days for 5 years. Once disease progression is documented, subjects will enter a survival follow up period every 6 months \pm 6 months for 3 years from the time of documented progression.

⁶Diagnosis and staging to include pathology report and AJCC 8th Ed staging. Standard biopsy to prove metastatic or recurrent disease should be available prior to registration

⁷Medical history to include smoking history and trial awareness question.

⁸Vital signs to include blood pressure, weight, and height (screening only) and ECOG performance status

⁹CMP to include sodium, potassium, chloride, creatinine, blood urea nitrogen; liver function tests (LFTs) to include AST, ALT, total bilirubin, alkaline phosphatase

¹⁰Prior to even cycles of drug.

¹¹For WOCBP: urine or serum β hCG, within 7 days prior to study registration. If a urine test is positive or cannot be confirmed as negative, a serum pregnancy test will be required.

¹²Tumor response assessment will be performed using standard-of-care imaging of all known sites of disease every 4th cycle starting with cycle 3; tumor imaging to be done at treatment discontinuation at discretion of investigator.

¹³Per standard of care, Pembrolizumab infusions will be given every 3 weeks and NKTR-214 administered on the same day each cycle.

¹⁴Fixed paraffin-embedded and/or frozen blocks/slides will be requested from the standard biopsy taken to prove metastatic or recurrent disease.

¹⁵Biopsy of the index tumor will be obtained by core, punch, or incisional biopsy on day 8 (\pm 5) of cycle 2.

¹⁶Serial blood samples for PBMC and serum will be collected prior to anti-PD-1 or NKTR-214 on Day 1 of Cycle 1, 2, and 3, on Day 8 of Cycle 1, 2, and 3, and at safety follow-up.

¹⁷Submission of unstained slides/blocks/frozen specimens for banking (if available).

APPENDIX B: CEREBROVASCULAR ACCIDENT ADVERSE EVENT MANAGEMENT ALGORITHM FOR THE COMBINATION OF BEMPEGALDESLEUKIN WITH CHECKPOINT INHIBITORS

The table below provides a management algorithm for possible signs of CVA and follow-up of CVA for patients treated with the combination of NKTR-214 with any checkpoint inhibitor. This general guideline constitutes guidance to the Investigator and may be supplemented by discussions with the Medical Monitor representing the Sponsor.

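### Section 11.3 gives two inconsistent evaluability rules for objective response; the text leans to the all-treated denominator but never rules out the re-evaluated set, which would raise the reported ORR

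*Combined protocol and SAP*

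**What the plan says.** Section 11.3 has two consecutive sentences on evaluability. The first reads "Any subject who receives at least one dose of NKTR-214 on this protocol will be evaluable for ORR". The second limits the set to those having "measurable disease who have received at least one cycle of treatment and have their disease re-evaluated will be evaluable for assessment of objective response". Neither is ranked above the other or given a separate use, and 11.3.1, which plans the primary analysis, names no denominator for the ORR or its 95% interval.

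Elsewhere:

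- Protocol Summary, primary objective: "Evaluate the objective response rate (ORR) to NKTR-214 in combination with anti-PD-1 therapy and palliative radiation in the efficacy-evaluable population". The secondary objectives use the same population for all the efficacy outcomes, ending "and duration of response with NKTR-214, anti-PD-1, and palliative radiation in the efficacy-evaluable population". It is not defined anywhere.
- Section 12.8.1: "The objective response rate is the proportion of all subjects with confirmed PR or CR according to RECIST 1.1".
- Section 11.2: "The null hypothesis will be rejected and superiority concluded if 8 or more responses are observed in 24 participants".
- Section 4.5.2: only subjects who leave before receiving NKTR-214 are replaced.

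**The concern.** ORR is the objective response rate, so both sentences of 11.3 concern the primary endpoint, and they describe different sets of subjects. A treated subject who is never rescanned belongs to the first set but not the second.

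Such a subject cannot have a confirmed CR or PR. Dropping that subject therefore shrinks the denominator and leaves the numerator alone. At stake is the headline estimate of a 24-patient single-arm trial that will be read against historical rates. While both rules stand, the choice between them could be made after the data are seen, and the re-evaluation condition can move the estimate only upward.

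**Working it through.** **1. The plan's own figure.** The plan gives no evaluability rate. Its only figure tied to a denominator is the cut-off in 11.2: 8/24 = 33.3%. The error rates attached there (type I error 0.04, power 0.8 at 44%) do not reproduce. The exact binomial for 8 or more of 24 gives 0.138 at 22% and 0.897 at 44%. That is a separate matter, and nothing below depends on it.

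**2. Which denominator the text favours.**

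| Place | Points to |
|---|---|
| 11.3, first sentence | all treated with NKTR-214 |
| 12.8.1 | all subjects; unassessed subjects are then non-responders by implication |
| 11.2 | 24 participants |
| 4.5.2 | the treated set, because a subject is no longer replaced once dosed |
| 11.3, second sentence | measurable disease, at least one cycle, and re-evaluated |
| Protocol Summary | undefined label, compatible with either sentence of 11.3 |

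The balance is for the all-treated set, but no passage says that the second sentence has some other purpose.

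**3. How a treated subject can go without a re-evaluation.** The first on-treatment scan is before cycle 3 (7.1.12). With 21-day cycles that is about day 42. Three routes lead out before then:

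- death;
- withdrawal from follow-up: "If the participant decides they no longer wish to participate in study follow-up, that visit will constitute the final study visit", and the procedures listed for that visit in 6.8 include no imaging;
- declining all radiotherapy after the cycle 1 dose, which under 5.8.3 takes the subject off the study. This counts here if it also ends imaging.

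Subjects who only stop treatment remain due for scans under 6.6 and 8.2.2, so most of them would be re-evaluated. A scan at the point of stopping is optional: "tumor imaging to be done at treatment discontinuation at discretion of investigator" (Appendix A, note 12).

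**4. Size.** Let x be the number of confirmed responders and k the number of treated subjects never re-evaluated.

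Reported ORR = x/(24 − k) = (x/24) × 24/(24 − k)

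The value of k is an assumption. Intervals are Clopper-Pearson, also an assumption, because 11.3.1 names no method. With x = 8:

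| k | n | Multiplier | ORR | 95% CI | Shift (points) |
|---|---|---|---|---|---|
| 0 | 24 | 1.000 | 33.3% | 15.6 to 55.3 | 0 |
| 2 | 22 | 1.091 | 36.4% | 17.2 to 59.3 | 3.0 |
| 3 | 21 | 1.143 | 38.1% | 18.1 to 61.6 | 4.8 |
| 4 | 20 | 1.200 | 40.0% | 19.1 to 63.9 | 6.7 |

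**5. Is that range of k reasonable?** Section 1.1.1 gives a median survival of 6 to 12 months. Assume exponential survival and take 42 days as 1.38 months. Expected deaths before the first scan are 24 × (1 − 2^(−1.38/m)):

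- m = 6: 24 × 0.147 = 3.5
- m = 12: 24 × 0.077 = 1.8

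This leans high for deaths. It treats every early death as unscanned and applies a general median to patients screened for ECOG 0-2 and organ function. Withdrawals and the radiotherapy route would add to it.

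**6. The measurable-disease condition.** Its direction is uncertain. Eligibility (4.1) requires an index tumor of at least 1 cm but not measurable disease, and 12.3 bars irradiated sites as target lesions unless all sites are irradiated. A subject without measurable target disease could still, in principle, reach CR on non-target lesions, so excluding such subjects need not raise the ORR.

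**The case against.** The strongest reply is that the documents already settle the matter. The first sentence of 11.3 uses the endpoint's own name, 12.8.1 takes a proportion of all subjects, 11.2 counts responses in 24 participants, and 4.5.2 makes those 24 the treated set. The second sentence can then be read as saying only who receives a response category, which fits the non-evaluable outcome in the 12.7 table. Most of this stands: it is the better reading. What it lacks is any text that gives the second sentence that limited role, or that ties the Protocol Summary's label to the first.

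The reply also points out that the plan tries to keep k small. Section 7.1.12 allows imaging whenever clinically indicated, 12.7 asks for progression to be documented even after treatment stops, and 4.5.2 asks for final assessments at withdrawal. That stands too. It bears on the size of the effect and not on the conflict between the two rules.

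Four stronger readings are tempting, and the documents do not support them:

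- *Unassessed subjects have no rule at all.* Section 12.8.1 implies that they are non-responders; only an explicit statement is missing.
- *The efficacy-evaluable label points to the restricted set.* It is no closer to the second sentence than to the first.
- *The trial's conclusion could change.* Rejection rests on a count of responses, which does not move when non-responders are dropped, and no test on a smaller n is planned. An ORR that passes 44% (for example 10/24 = 41.7% becoming 10/22 = 45.5%) triggers nothing in the plan.
- *The whole second rule biases upward.* That is shown only for its re-evaluation condition.

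**Conclusion.** The point holds as an inconsistency in the rules for the primary endpoint. It is not an open denominator: the text favours all treated subjects. The conflict matters because the alternative is left available and its re-evaluation condition can only raise the estimate. With 8 responders and an assumed 0 to 4 treated subjects never rescanned, the rise is 0 to 6.7 percentage points, against a 95% interval about 40 points wide. If every treated subject is rescanned, that condition has no effect. Only the reported ORR and its interval are affected. It should be fixed, with moderate confidence, because the surrounding text already leans the right way and the number lost is assumed.

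**What to change.** In 11.3, state that all subjects who receive at least one dose of NKTR-214 form the primary ORR denominator, and that subjects with no post-baseline disease assessment, or who cannot be assessed for response, count as non-responders. Keep the second sentence only as a labelled sensitivity set (measurable disease and re-evaluated), and report how many treated subjects it leaves out. In the Protocol Summary, define the efficacy-evaluable population as the all-treated set, with duration of response analysed in responders.

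The cost is wording only, with no added patients, visits or scans. The downside is a reported ORR somewhat lower than under the second sentence: with 8 responders, by 3.0 points if 2 subjects are lost, 4.8 if 3, and 6.7 if 4.
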